## 7.7.4 Vital Signs

Analyses will be performed for vital sign safety data collected at baseline and from first exposure to any study drug to 30 days after last dose (latest of any study drug) or up to the safety follow-up visit date, whichever is later. Summary statistics (mean, standard deviation, median, minimum and maximum) will be produced for vital signs at baseline, post-baseline values from the last visit, minimum and maximum post-baseline values, and changes of these post-baseline values from baseline.

In order to be included in the table, a subject must have at least one post-baseline value for the given time point.

#### 7.7.5 ECOG Performance Score

Change of ECOG score from baseline to the maximum score during the period from first exposure to any study drug to 30 days after last dose (latest of any study drug) or up to the safety follow-up visit date, whichever is later, will be provided as shift tables.

#### 7.7.6 Electrocardiogram (ECG)

Baseline in QT, heart rate, QTcB, QTcF, PR, RR, and QRS will be summarized by abnormality and clinical significance using Sponsor reporting standards. Listings of subjects with any single value

Version 1.0: 31Mar2022

>480 msec will also be produced for QTcF and QTcB.

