1.3 CLINICAL EXPERIENCE WITH ACALABRUTINIB

1.3.1 Pharmacokinetics and Pharmacodynamics of Acalabrutinib in Healthy Volunteers

Acalabrutinib has been studied in 10 clinical trials in healthy volunteers. In humans, acalabrutinib has a short pharmacokinetic (PK) half-life with a long-lasting pharmacodynamic (PD) effect due to covalent binding to BTK after oral administration.

In an FIH study in subjects with R/R CLL, acalabrutinib plasma time to maximum concentration (T_{max}) values were between 0.5 and 1.0 hour for all dose cohorts (2.5 mg twice per day [BID] to 100 mg once per day [QD]), and the mean half-life ranged from 0.97 to 2.1 hours. Acalabrutinib has an absolute oral bioavailability of 25%, is best taken with water, can be taken with or without food, and does not accumulate in plasma upon repeat-dose administration. In healthy subjects, exposure was generally linear over the dose range of 15 mg to 100 mg and slightly greater than proportional between 100 mg and 400 mg. Variability in exposure to acalabrutinib is mainly due to a combination of pH-dependent absorption, and predominantly CYP3A-mediated metabolism.

For more detailed information on acalabrutinib clinical pharmacology studies, please refer to the Acalabrutinib Investigator Brochure.

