4.1.9 Electrocardiogram

Subjects should be in supine position and resting for ≥10 minutes before study-related ECGs. At screening, results from the site's ECG machine (12-lead; triplicates taken ≥1 minute apart) will be averaged to determine eligibility and must meet the eligibility criteria of QTcF ≤480 msec. A single ECG will be performed at the end of treatment and safety follow-up visits.

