- g. The physical examination includes height (screening only) and weight, and examination of the skin, eyes, ears, nose, throat, lungs, heart, abdomen, extremities, musculoskeletal, nervous, lymphatic system, and general appearance. The lymphatic system examination will include examination of palpable lymph nodes and spleen and liver below the costal margin on the respective side. Only physicians, physician assistants, or oncology nurse practitioners should perform the lymphatic system examination. As much as possible, the same person should perform all the lymphatic exams for a given subject.
- h. Vital signs (blood pressure, pulse, respiratory rate, and temperature) will be assessed after the subject has rested in the sitting position.
- i. Subjects should be in supine position and resting for ≥10 minutes before study-related ECGs. A 12-lead ECG will be performed in triplicate (≥1 minute apart) at screening. The calculated QTcF average of the 3 ECGs must be ≤480 ms for eligibility. If results from an unscheduled ECG are abnormal and considered clinically significant at any time, then an electrolyte panel (i.e., calcium, magnesium, and potassium) must be obtained to coincide with the ECG testing.
- j. Tumor assessments: 1) An endoscopy for subjects with gastric MALT lymphoma is required within 90 days before the dose of study drug. 2) A pretreatment CT scan with contrast (unless contraindicated) is required of the chest, abdomen, and pelvis and any other disease sites (e.g., neck) within 30 days before the first dose of study drug. A pretreatment PET/CT scan within 60 days before the first dose of study drug. During treatment, CT scans will be performed for tumor assessments every 3 cycles (12 weeks, ±7 days) starting at Day 1 of Cycle 4, Cycle 7, Cycle 10, and Cycle 13, and then every 24 weeks thereafter or more frequently at the investigator's discretion. 3) A bone marrow aspirate/biopsy is required within 90 days before the first dose of study drug and is optional at the end of treatment for molecular profiling to discover mechanisms of resistance to study treatment. Bone marrow aspirate/biopsy (if involved by lymphoma at baseline), endoscopy (for subjects with gastric MALT), and PET/CT to confirm CR per clinical guidelines (see Section 4.2). When possible, extra bone marrow tissue may be used for pharmacodynamic evaluation. 4) At all other visits, tumor assessments will be performed by physical examination and laboratory test results.

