**6.1 Definitions** 

6.1.1 Definition of Baseline and Post-Baseline Value

Baseline is defined as the last measurement taken prior to the first dose of any study drug. A post-

baseline value is defined as a measurement taken after the first dose of any study drug.

For assessments on the day of first dose where time is not captured, a nominal pre-dose indicator,

if available, will serve as sufficient evidence that the assessment occurred prior to first dose.

Assessments on the day of first dose where neither time nor a nominal pre-dose indicator are

captured will be considered prior to first dose if such procedures are required by the protocol to be

conducted before first dose.

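### SAP 7.7.6 summarises ECG intervals at baseline only, and its >480 msec listing does not separate readings taken before the first dose from those taken after it

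*SAP*

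**What the plan says.** SAP 7.7.6 plans two ECG outputs. The first is a summary: "Baseline in QT, heart rate, QTcB, QTcF, PR, RR, and QRS will be summarized by abnormality and clinical significance", following sponsor reporting standards that the SAP does not describe. The second is a listing, in a sentence that runs over a page break: "Listings of subjects with any single value" and then ">480 msec will also be produced for QTcF and QTcB".

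The protocol collects more than this uses. For Parts 2 and 3, footnote i of Appendices 5 and 6 says "A 12-lead ECG will be performed in triplicate (≥1 minute apart) at screening", and "The calculated QTcF average of the 3 ECGs must be ≤480 ms for eligibility". Protocol 4.1.9 adds "A single ECG will be performed at the end of treatment and safety follow-up visits". Protocol 4.3 places the safety follow-up visit 30 (+7) days after the last dose, and only until the final data cut-off. Neither schedule has an ECG during a treatment cycle.

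SAP 6.1.1 gives the general baseline rule: "Baseline is defined as the last measurement taken prior to the first dose of any study drug". It says nothing about replicate readings.

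**The concern.** Safety is the primary objective of Part 3 and a secondary objective of Part 2, and ventricular arrhythmia is an adverse event of special interest (Protocol 6.2.3; SAP Appendix 1). Subjects have ECGs after treatment, yet the plan specifies no table for them. The one output that can contain post-dose readings is filtered at a fixed threshold and is open to screening readings as well. A count of listed subjects could therefore be taken as a count of post-dose QTc prolongation when some entries predate any study drug. In the other direction, a large rise that stays below 480 msec would be in neither ECG output of SAP 7.7.6.

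**Working it through.** The plan states no figure for the ECG analysis, so there is none to reproduce. The check sets the schedule against the planned outputs, then asks whether a pre-dose reading can enter the listing.

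**1. Scheduled readings per subject (Protocol 4.1.9, Appendices 5 and 6)**

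| Time | Readings | In the SAP 7.7.6 summary? | Eligible for the >480 listing? |
|---|---|---|---|
| Screening | 3 | yes, as baseline | yes |
| During treatment cycles | 0 scheduled | – | unscheduled ECGs only |
| End of treatment | 1 | no | yes |
| Safety follow-up | 1 | no | yes |

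Total 3 + 1 + 1 = 5, so 3/5 = 60% of scheduled readings are pre-dose. A subject still on treatment at the final data cut-off has only the three screening readings. Unscheduled ECGs are foreseen at any time (Protocol 4.1.12; Appendices 5 and 6, footnote i) and for symptoms of atrial fibrillation (Protocol 3.7.1). The listing would take these in, so two is not an upper limit on post-dose readings.

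**2. Comparison with neighbouring SAP sections**

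| Data | Post-baseline values and change | Shift table |
|---|---|---|
| Laboratory (7.7.3) | yes | yes |
| Vital signs (7.7.4) | yes | no |
| ECOG (7.7.5) | – | yes |
| ECG (7.7.6) | none | none |

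**3. Can an eligible subject be listed before dosing on QTcF?** Yes. Screening readings of 470, 472 and 486 msec have mean 1428/3 = 476, which meets the criterion, and one reading exceeds 480.

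How often depends on the true QTcF, μ, and the within-subject SD, σ. The documents give neither, so both are assumed here. With normal readings, let A = 1 − Φ((480 − μ)/σ)³, the chance that any of three exceeds 480, and B = 1 − Φ(√3(480 − μ)/σ), the chance that the mean does. Given a mean ≤480, the chance that at least one reading exceeds 480 is (A − B)/(1 − B). For μ = 470 and σ = 10: A = 1 − 0.8413³ = 0.4045, B = 0.0416, giving 0.3629/0.9584 = 0.38.

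| Assumed σ (msec) | μ = 450: any of 3 screening readings >480 | μ = 470: any of 3 screening readings >480 | μ = 470: any of 2 later readings >480, no drug effect |
|---|---|---|---|
| 5 | 0% | 7% | 4% |
| 10 | 0.4% | 38% | 29% |
| 15 | 7% | 52% | 44% |

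For subjects near the threshold, three screening readings are more likely to trigger a listing than two later readings with no drug effect. Well below it, either is rare.

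**4. The same question for QTcB.** Eligibility in Parts 2 and 3 is on QTcF only. Since QTcF = QT/RR^(1/3) and QTcB = QT/RR^(1/2), QTcB = QTcF × RR^(−1/6). At 80 beats/min, RR = 60/80 = 0.75 s and the factor is 1.0491, so QTcB reaches 480 at QTcF = 480/1.0491 = 457.5 msec. At 100 beats/min the factor is 1.0889 and the figure is 440.8 msec. A subject well inside the QTcF criterion can be listed for QTcB at screening.

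**5. What the threshold misses.** A QTcF rising from 400 to 470 msec (+70) does not exceed 480, so it is not listed, and no change-from-baseline table would record it.

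**The case against.** The strongest reply is that little is lost. Protocol 5.5.1 promises laboratory, vital-sign and physical-examination summaries but no ECG summary, so the SAP breaks no commitment. The safety endpoints are based on adverse events. QT prolongation is not among the acalabrutinib risks in Protocol 3.7.1. Torsade de pointes and the other ventricular arrhythmias are captured by preferred term and tabulated (SAP 7.7.2, Appendix 1). SAP 6 provides for data listings by arm and subject, which on a plain reading include ECG data. The columns of the >480 listing are not specified; if visit or date is shown, a screening value can be told from a later one. The sponsor standards cited in 7.7.6 may add detail.

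All of this stands, and it limits the point. None of it supplies a post-baseline summary or confines the listing to post-dose values.

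Several stronger readings are tempting, and the documents do not support them:

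- *The ECG analysis is incapable of revealing a QTc change.* A post-dose value above 480 would be listed, and individual changes could be traced if the general listings carry ECG data. What is missing is a summary.
- *A rise below 480 msec is invisible.* It would be in no planned summary table, but SAP 6 listings may show it.
- *No more than two post-dose readings exist.* That is true of scheduled ECGs only.
- *SAP 6.1.1 makes the third screening reading the baseline.* The section does not address triplicates; the fair statement is that no averaging rule is given.
- *The safety follow-up ECG is drug-free.* Protocol 1.3.1 says "the mean half-life ranged from 0.97 to 2.1 hours", but that is parent acalabrutinib in a CLL study. The documents give no half-life for the active metabolite, rituximab or lenalidomide.

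**Conclusion.** The concern holds as a gap in the specified summaries. Read as written, SAP 7.7.6 puts neither of the two scheduled post-dose ECGs into a table, and its listing can include subjects on screening readings alone. This rests on the text of 7.7.6 meaning what it says. The sentence is awkward, and words may have been lost in drafting; if so, the wording needs the same repair.

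The size is modest. The table is missing for every treated subject who has an end-of-treatment or safety follow-up ECG, but clinical arrhythmias are reported elsewhere. The effect on the listing is negligible for subjects far below 480 msec and material near it; the percentages above depend on assumed values of μ and σ. The QTcB result needs no assumption about variability, only a heart rate.

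A reader might go further and expect the added tables to settle whether treatment prolongs QTc. They would not: no ECG is scheduled during cycles, and each part is small and has no untreated control. That limit comes from the schedule and should be stated in the report.

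**What to change.** Rewrite SAP 7.7.6 to:

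1. define ECG baseline as the mean of the screening triplicate, as an exception to SAP 6.1.1;
2. summarise observed value and change from baseline, for at least QTcF, heart rate, PR and QRS, at end of treatment and at safety follow-up;
3. add a table of baseline against maximum post-baseline QTcF category, with the protocol's 480 msec as one of the cut-points;
4. restrict the >480 listing to post-baseline values, or flag each value as pre- or post-dose and as scheduled or unscheduled, with time since last dose;
5. state that QTc during treatment cycles is not systematically assessed, so that end-of-treatment and follow-up values are not read as on-treatment evidence.

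The cost is a change to the SAP wording and one or two extra tables from ECGs already collected. No visit, procedure or protocol amendment is needed.

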7.8 PK Parameters

For Part 2, no PK sample was collected. Therefore, there will be no PK analysis for Part 2.

For Part 3, plasma concentrations of acalabrutinib and ACP-5862 will be tabulated for each subject by arm, visit, and timepoint. Descriptive statistics (n, mean, standard deviation, %CV, median, minimum, maximum) of plasma concentrations of acalabrutinib (and metabolite(s), if applicable) will be presented by visit.

A by-subject listing of plasma concentrations will be provided. This listing will include: subject identifier, visit, unique sample ID, planned time post dose, actual time post dose and concentration.

8. CHANGES FROM PROTOCOL-SPECIFIED ANALYSES

In the definition for the efficacy-evaluable population, it was further specified that the ≥1 response assessment (as required per CSP Section 5.3) must have overall response not "unknown" or missing.

CSP Section 5.5.4 specifies that PFS, TTNT, and OS will be calculated using the first dose date of acalabrutinib as the reference date for time to event. However, as this study includes combination therapy, SAP Sections 7.6.3-7.6.5 were changed to specify that the date of first dose of any study drug will be used as the reference date for time to event.

9. AD HOC ANALYSES

In addition to the analyses described in earlier sections for the CSR, the following ad hoc analyses are planned to support the reporting of results in a manuscript and/or congress presentation(s). Further ad hoc analyses may be conducted as needed.

9.1 Ad Hoc Analyses for Part 2 (MZL)

9.1.1 Subgroup Analyses for ORR

A subgroup analysis will be performed for ORR in which the number and percentage of subjects in each best overall assessment category will be presented by treatment arm and MZL subtype.

Additionally, ORR and the corresponding 2-sided 95% confidence interval will be calculated for each subgroup listed below and displayed in a forest plot, following the method described in Section 7.6.1:

- MZL subtype
- Age group
- ECOG performance score
- Bulky disease
- Bone marrow involvement
- Number of prior systemic regimens
- Type of prior anticancer therapy

The subgroup analyses will be performed in both the all-treated population and the efficacyevaluable population.

#### 9.1.2 Swimmer Plot for Overall Response

A swimmer plot will be generated for time from first dose of any study drug to each overall response (CR, PR, SD, or PD). MZL subtype will be indicated for each subject on the plot. Death and treatment status on acalabrutinib will be shown (ongoing on acalabrutinib or discontinued acalabrutinib, with reason for discontinuation).

#### 9.2 Ad Hoc Analyses for Part 3 (FL)

Subgroup analyses will be performed for the efficacy endpoints ORR, DOR, and PFS. The analyses described in Sections 7.6.1-7.6.3 (with exception of COVID-19 sensitivity analyses) will be repeated in the following subgroups:

- Refractory to any prior regimen containing anti-CD20 antibodies (yes)
- Double refractory (yes)

Additionally, ORR, median DOR, median PFS and the corresponding 2-sided 95% confidence intervals will be calculated for each subgroup listed below and displayed in forest plots, following the methods described in Sections 7.6.1-7.6.3:

- Ann Arbor stage at study entry
- Age group
- ECOG performance score
- Bulky disease

# ACE-LY-003 Parts 2-3 Statistical Analysis Plan Version 1.0: 31Mar2022

- Bone marrow involvement
- Number of prior systemic regimens
- Type of prior anti-cancer therapy
- FLIPI score
- High tumor burden per GELF criteria
- Refractory versus relapsed
- Refractory to any prior regimen containing anti-CD20 antibodies
- Double refractory

The subgroup analyses will be performed in the all-treated population and may be performed in the efficacy-evaluable population.

#### 11. APPENDICES

# APPENDIX 1 – Definition of Adverse Event of Special Interest and Events of Clinical Interest

The below definitions are based on MedDRA version 24.1 and will be updated as appropriate based on the most current MedDRA version used at the time of the data extract.

# 1. Adverse Event of Special Interest (AESI)

AESI Category	Definition
Ventricular arrhythmias	PT Torsade de pointes
	PT Ventricular arrhythmia
	PT Ventricular extrasystoles
	PT Ventricular fibrillation
	PT Ventricular flutter
	PT Ventricular tachyarrhythmia
	PT Ventricular tachycardia
Suspected transmission of an infectious agent	PT Product cleaning inadequate
via product*	PT Product contamination
	PT Product contamination chemical
	PT Product contamination microbial
	PT product sterility lacking
	PT Transmission of an infectious agent via
	product
	
 
PT Suspected product contamination
 

\*For subjects taking study treatment containing biologic products, e.g. rituximab.

#### 2. Events of Clinical Interest

The Events of Clinical Interest (ECIs) have been identified based on preclinical findings, emerging data from clinical studies relating to acalabrutinib, and pharmacological effects of approved Bruton's tyrosine kinase (BTK) inhibitors. The adverse events (AEs) selected for dedicated analysis were evaluated using Standardized MedDRA Queries (SMQs), where available, by System Organ Classes (SOCs), or by Sponsor-defined baskets of MedDRA Adverse Event Grouped Terms.

Category	Subcategory	Definition
Cardiac events		SOC Cardiac disorders
	Atrial fibrillation	PT Atrial fibrillation
		PT Atrial flutter
	Ventricular	PT Torsade de pointes
	tachyarrhythmias	PT Ventricular arrhythmia
		PT Ventricular extrasystoles
		PT Ventricular fibrillation
		PT Ventricular flutter
		
 
PT Ventricular tachyarrhythmia
 

		PT Ventricular tachycardia
Cytopenias –		SMQ Haematopoietic erythropenia [narrow +
Anemia		broad]
Cytopenias – Leukopenia		SMQ Haematopoietic leukopenia [narrow + broad]
	Neutropenia	PT Band Neutrophil count decreased
		PT Band neutrophil percentage decreased

		•	PT Cyclic neutropenia
		•	PT Febrile Neutropenia
		•	PT Granulocyte count decreased
		•	PT Granulocyte percentage decreased
		•	PT Idiopathic neutropenia
		•	PT Neutropenia
		•	PT Neutropenic infection
		•	PT Neutropenic sepsis
		•	PT Neutrophil count decreased
		•	PT Neutrophil percentage decreased
	Other leukopenia	•	SMQ Haematopoietic leukopenia [narrow + broad] excluding PTs for neutropenia above
Cytopenias - Thrombocytopenia		•	SMQ Haematopoietic thrombocytopenia [narrow + broad]
Hemorrhage		•	SMQ Haemorrhage terms (excl laboratory terms)
	Major hemorrhage	•	As per definition (see Section 3 below)
Hepatotoxicity		•	SMQ [narrow] Hepatic failure, fibrosis and cirrhosis and other liver damage-related conditions
		•	SMQ [narrow] Hepatitis, non-infectious
		•	SMQ [narrow] Liver related investigations signs
Hypertension		•	SMQ Hypertension [narrow]
Infections		•	SOC Infections and infestations
Interstitial lung disease/Pneumonitis		•	SMQ [narrow] Interstitial lung disease
Second primary malignancies		•	SMQ Malignant tumours (including Haematological malignant tumours SMQ and Non-haemoatological malignant tumours SMQ) SMQ Malignant lymphomas [narrow] SMQ Myelodysplastic syndrome [narrow]
	Second primary malignancies (excluding non melanoma skin)	•	The above excluding PTs mapping to HLT Skin neoplasms malignant and unspecified (excluding melanoma)
Tumor lysis syndrome		•	PT Tumour lysis syndrome

HLT=High-Level Term; PT=Preferred Term; SOC=System Organ Classes; SMQ=Standardized MedDRA Query.

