Lenalidomide is indicated for subjects with multiple myeloma, myelodysplastic syndrome (MDS) with deletion 5q, and MCL (Revlimid package insert). The monotherapy dose ranges from 10 mg for MDS to 25 mg for MM and MCL. In the study combining lenalidomide with rituximab for R/R FL, lenalidomide was started at 15 mg in Cycle 1 and then escalated to 20 mg in Cycles 2 through 12 for 21 of 28 days with an ORR of 76% in combination with rituximab compared with 53% for lenalidomide alone (Leonard et al. 2015). In untreated patients with FL, ibrutinib was added to lenalidomide and rituximab. Similarly, the starting dose of lenalidomide was 15 mg with dose escalated to 20 mg for 21 of 28 days with rituximab and ibrutinib. The combination was not more efficacious than rituximab-lenalidomide. There were no protocol-defined DLTs; however, increased toxicity (rash 82%, diarrhea 64%, and fatigue 59%) and dose modifications were required in this untreated FL group, so a subsequent study is not planned. Of note, in patients with previously untreated FL receiving ibrutinib in combination with rituximab and lenalidomide, patients received 90% of the expected dose intensity of rituximab, 93% of ibrutinib, and only 64% of lenalidomide (Ujjani et al. 2016). Given this experience, Part 3 of this study will start with 15 mg of lenalidomide to be combined with acalabrutinib and rituximab. For Part 3, lenalidomide will be given on Days 1 through 21 of a 28-day cycle up to 12 cycles or until disease progression or an unacceptable toxicity

occurs, whichever comes first.

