3.5.5 Definition of Dose-limiting Toxicity (Part 3)

A DLT will be defined as the occurrence of any of the following study drug-related AEs

during the DLT review period. (Note: AEs clearly related to disease progression or the subject's medical history and associated comorbidities considered by the investigator to be unrelated to study drugs, will not be considered DLTs. Infusion reactions clearly associated with rituximab infusion will not be considered DLTs.):

- 1. Non-hematologic DLTs include:
 - a) Grades 3 or 4 nausea, vomiting, or diarrhea lasting >7 days despite optimal antiemetic or antidiarrhea management or any Grade 3 or Grade 4 toxicity
 - b) Any grade Stevens-Johnson syndrome or toxic epidermal necrolysis
 - c) AST or ALT >3 × ULN concurrently with total bilirubin >2 × ULN
 - d) Clinical TLS not resolving to baseline after a 2-week treatment delay
- Exceptions are deep vein thrombosis (DVT), correctable electrolyte
 abnormalities, or Grade 3 or Grade 4 laboratory abnormalities lasting ≤7 days;
 Grades 3 or 4 fatigue, anorexia, non-neutropenic fever, Grade 3 rash resolving to
 Grade 2 within 10 days (allowed therapy with steroids)
- 2. Hematologic DLTs include:
 - a) Grade 3 or Grade 4 neutropenia with fever ≥38.5°C or infection, or Grade 4 neutropenia lasting >7 days despite adequate granulocyte-colony stimulating factors (G-CSF) use
 - b) Grade 3 or Grade 4 thrombocytopenia with hemorrhage. If thrombocytopenia improves to Grade ≤2 or to ≥80% of the baseline value within 28 days, without a platelet transfusion, this will not be considered a DLT
 - c) Any Grade 4 hematologic toxicity unrelated to the underlying disease
- 3. Any study drug-related Grade 5 AE
- 4. Any study drug-related toxicity leading to an individual drug dose delay of >21 consecutive days for acalabrutinib or >14 consecutive days for lenalidomide will be considered as a DLT. Subjects should receive at least one dose of rituximab in Cycle 1 to be evaluable for a DLT.

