3.7.3 Risks Associated with Lenalidomide (Revlimid) Treatment

Cases of PML, including fatal cases, have been reported in subjects treated with lenalidomide in combination with immunosuppressive therapy including dexamethasone. Signs and symptoms of PML may include cognitive and behavioral changes, language disturbances, visual disturbances, sensory deficits, weakness, and coordination and gait difficulties. If PML is suspected, hold further treatment with lenalidomide until PML is excluded. If PML is confirmed, lenalidomide will be permanently discontinued.

For complete information refer to the local label Reference Safety Information for lenalidomide (Revlimid package insert) for this study. Also refer to Section 3.5.7 in this protocol for specific dose modification and discontinuation guidelines.

Contraindications

Pregnancy

Lenalidomide can cause fetal harm when administered to a pregnant female.

Lenalidomide is contraindicated in females who are pregnant per the package insert.

Allergic Reactions

Lenalidomide is contraindicated in patients who have demonstrated hypersensitivity (e.g., angioedema, Stevens-Johnson syndrome, toxic epidermal necrolysis) to lenalidomide.

Revlimid capsules contain lactose. The risk-benefit of Revlimid treatment should be evaluated in subjects with lactose intolerance per package insert.

Warnings and Precautions

Embryo-fetal Toxicity

If lenalidomide is used during pregnancy, it may cause birth defects or embryo-fetal death (boxed warning). Pregnancy must be excluded before start of treatment.

Hematologic Toxicity

Lenalidomide can cause significant neutropenia and thrombocytopenia (boxed warning).

Venous and Arterial Thromboembolism

Venous thromboembolic events (deep vein thrombosis and pulmonary embolism) and arterial thromboembolic events (myocardial infarction and stroke) are increased in patients treated with lenalidomide and seen in patients treated for multiple myeloma (boxed warning).

Mvocardial Infarction

Myocardial infarction has been reported in patients receiving lenalidomide, particularly in those with known risk factors and within the first 12 months when used in combination with dexamethasone. Patients with known risk factors – including prior thrombosis – should be closely monitored, and action should be taken to try to minimize all modifiable risk factors (eg. smoking, hypertension, and hyperlipidemia).

Increased Mortality

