# 2.2 Part 3 (Follicular Lymphoma)

#### 2.2.1 Primary Objective

• To characterize the safety of acalabrutinib in combination with rituximab and lenalidomide in subjects with R/R follicular lymphoma (FL)

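### For Part 3, the SAP's grouped safety events follow acalabrutinib and its drug class, so no planned table gives the proportion of subjects with any thromboembolic event or any rash

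*SAP*

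**What the plan says.** SAP Section 2.2.1 gives the Part 3 primary objective: "To characterize the safety of acalabrutinib in combination with rituximab and lenalidomide in subjects with R/R follicular lymphoma (FL").

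The SAP's grouped safety summaries are the two lists in Appendix 1, which Section 7.7.2 tabulates as subject incidence.

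- **Adverse events of special interest.** There are two categories: ventricular arrhythmias, and "Suspected transmission of an infectious agent" via product. The second is marked for subjects taking a biologic, with rituximab as the example.
- **ECIs.** These "have been identified based on preclinical findings, emerging data from clinical studies relating to acalabrutinib, and pharmacological effects of approved" BTK inhibitors. The categories are cardiac events, anemia, leukopenia, thrombocytopenia, hemorrhage, hepatotoxicity, hypertension, infections, interstitial lung disease/pneumonitis, second primary malignancies and tumor lysis syndrome. The cardiac category is "SOC Cardiac disorders", with subcategories only for atrial fibrillation and ventricular tachyarrhythmias. There is no separate list for Part 3.

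All other adverse events are tabulated by system organ class and/or preferred term (SAP Section 7.7.1).

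The protocol treats both missing harms as relevant to Part 3. Section 3.7.3 states, as a boxed warning, that venous events (deep vein thrombosis, pulmonary embolism) and "arterial thromboembolic events (myocardial infarction and stroke) are increased in patients treated with lenalidomide". Section 3.5.1 says that subjects on lenalidomide should receive low-dose aspirin. Section 3.3 reports "increased toxicity (rash 82%, diarrhea 64%, and fatigue 59"%) with the ibrutinib triplet, and Section 1.7 repeats the rash figure. Severe skin reactions are warned of for rituximab (Section 3.7.2) and for lenalidomide (Section 3.7.3).

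**The concern.** A Part 3 safety report should be able to say how many subjects had any thromboembolic event and how many had any rash. Each is a family of diagnoses that will be coded to several preferred terms. A row for one term understates the family. A system organ class row mixes in unrelated events and need not contain the whole family. Myocardial infarction, for instance, would presumably fall in the cardiac ECI, but nothing there separates it as a thromboembolic event or joins it to deep vein thrombosis, pulmonary embolism or stroke.

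Two features of the plan make the omission look unintended. The special-interest list was extended for one partner drug, rituximab, with no matching addition for lenalidomide. And hemorrhage has a grouped category, a major-event definition and a narrative criterion, while the thromboembolism that the aspirin is meant to prevent has none of these. The report would therefore summarize only one side of that balance.

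The stake is the quality of a descriptive primary result. A basket of terms chosen after the data have been seen is weaker evidence on a primary objective than one fixed beforehand.

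**Working it through.** **1. The plan's own detection figures.** The documents give the probability of seeing at least one adverse event only for Part 1 (Protocol Section 5.2). The formula is 1 − (1 − p)^n.

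- n = 36: 1 − 0.95^36 = 0.842 and 1 − 0.90^36 = 0.978. The plan states 84% and 98%.
- n = 12: 1 − 0.95^12 = 0.460 and 1 − 0.90^12 = 0.718. The plan states 46% and 72%.

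All four reproduce. The same formula at the Part 3 sizes (26 to 32, SAP Section 3.2) and rates of 5% and 10% gives 74% and 94% for n = 26, and 81% and 97% for n = 32. Grouping changes none of these sample sizes.

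**2. Harms named in the protocol against SAP categories.**

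| Harm flagged for lenalidomide or the triplet | Protocol section | Grouped category in SAP Appendix 1 |
|---|---|---|
| Neutropenia, thrombocytopenia | 3.7.3 | Yes |
| Hepatotoxicity | 3.7.3 | Yes |
| Second primary malignancies | 3.7.3 | Yes |
| Tumor lysis syndrome | 3.7.3 | Yes |
| Venous and arterial thromboembolism | 3.5.1, 3.7.3 | None |
| Rash, severe cutaneous reactions | 1.7, 3.3, 3.7.3 | None |

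The list does overlap with lenalidomide's warnings. The gap is confined to the last two rows.

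**3. What term-level rows can say.** If the rows for k terms show x1, …, xk subjects out of n, the number with any of the events lies between max(xi) and the smaller of n and Σxi. The rows do not say where in that range it falls, because one subject may appear in several. For example, two terms at 5% each are compatible with any union from 5% to 10%. Three terms at 3.3% each are compatible with 3.3% to 10%. The sum is exact only when no subject has more than one term.

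**4. What splitting costs at this sample size.** Assume a 10% grouped rate divided equally over two or three terms that do not overlap. The rate and the split are assumptions, since the documents give neither. Let X be the number of subjects affected.

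- Grouped: P(X ≥ 2) = 1 − 0.9^n − n(0.1)(0.9)^(n−1).
- One term named in advance: the same formula with p = 0.05 (two terms) or p = 0.1/3 (three terms).
- At least one of the k terms reaching two subjects: 1 − Σ_{j=0..k} C(k,j) · n!/(n−j)! · (0.1/k)^j · 0.9^(n−j).

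| n | Grouped | At least one term (k = 2 / k = 3) | One named term (k = 2 / k = 3) |
|---|---|---|---|
| 26 | 75% | 62% / 52% | 38% / 21% |
| 32 | 84% | 74% / 65% | 48% / 29% |

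The middle column is the fair comparison, because a reader of the table sees every row. On these assumptions the loss is about 10 to 22 percentage points (84 − 74 = 10; 0.749 − 0.525 = 0.224 for n = 26, k = 3).

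**The case against.** The best defense is that no commitment is broken. The protocol and SAP promise the type, frequency, severity, timing and relatedness of adverse events. Neither promises a grouped rate for thromboembolism or rash. Part 3 is descriptive and not powered, and no test or dose rule uses such a rate. Deaths, serious events and events leading to discontinuation all get narratives under SAP Appendix 2. Data are listed by subject (SAP Section 6), and further ad hoc analyses are allowed (SAP Section 9). All of this stands. It limits the size of the point but does not supply the prespecified proportion.

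Several stronger readings are tempting, and the documents do not support them.

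- **That the rates could not be obtained.** In 26 to 32 subjects they can be counted from the listings. They are unplanned, not unobtainable.
- **That every deep vein thrombosis escapes the dose-limiting toxicity count.** The exceptions in Protocol Section 3.5.5 open "Exceptions are deep vein thrombosis (DVT), correctable electrolyte" abnormalities, with no grade stated for the thrombosis. But they sit under the non-hematologic criteria. A related event that is fatal (item 3), or that delays acalabrutinib by more than 21 consecutive days or lenalidomide by more than 14 (item 4), still counts. Pulmonary embolism is not excepted.
- **That thromboprophylaxis is mandatory.** Protocol Section 3.5.1 says should, and leaves additional prophylaxis for high-risk subjects to the investigator.
- **That a rash basket would allow comparison with the cited 82%.** That study enrolled previously untreated follicular lymphoma, whereas Part 3 enrolls relapsed or refractory disease. The study's definition of rash is not in the documents.
- **That the list serves acalabrutinib alone.** Its stated basis includes the BTK-inhibitor class, and four harms in the table above are shared with lenalidomide.

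**Conclusion.** The point holds in limited form. SAP Appendix 1 has no Part 3 category for venous and arterial thromboembolism or for rash and severe cutaneous reactions. No prespecified output therefore gives the proportion of subjects with any event of either kind, although the primary objective is the safety of the triplet and the protocol flags both harms. This conclusion comes from reading the lists and depends on no assumed rate. The 10 to 22 point loss is only an illustration and rests on the assumed 10% rate, the equal split and no overlap between terms.

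It is a worthwhile, low-cost improvement. It changes no sample size, test or trial conduct.

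Whether deep vein thrombosis should be dose-limiting is a clinical rule on which no position is taken. The sponsor should reconcile the exception in Protocol Section 3.5.5 with Sections 3.5.1 and 3.7.3.

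**What to change.** Add two categories for Part 3 to SAP Appendix 1, Section 2, in the format it already uses (a standardized MedDRA query or a sponsor-defined basket of preferred terms):

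1. **Thromboembolic events**, with venous and arterial subcategories.
2. **Rash**, with a severe cutaneous reactions subcategory.

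Report subject incidence at any grade and at Grade 3 or higher, counting each subject once per category. State that all such adverse events are included whether or not they met the dose-limiting toxicity definition. Fix the term lists before database lock.

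The cost is appendix wording and a few extra rows in an existing table. The adverse events are already collected and coded, so no new data are needed.
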